10.3 Procedure for Breaking the Randomisation Code

Emergency treatment code breaks should only be undertaken when it is essential to treat the subject safely and efficaciously. Most often, investigational treatment discontinuation and knowledge of the possible treatment assignments are sufficient to treat a study subject who presents with an emergency condition. Emergency code breaks are performed using the IRT. When the investigator contacts the system to break a treatment code for a subject, he/she must provide the requested subject identifying information and confirm the necessity to break the treatment code for the subject. The investigator will then receive details of the investigational drug treatment for the specified subject and a fax or email confirming this information. The system will automatically inform the ICON site monitor, the medical monitor, and the ICON Project Manager that the code has been broken, but no treatment assignment will be communicated.

It is the investigator's responsibility to ensure that there is a procedure in place to allow access to the IRT in case of emergency. The investigator will inform the subject how to contact his/her backup in cases of emergency when he/she is unavailable. The investigator will provide the protocol number, investigational treatment name if available, subject number, and instructions for contacting the local entity which has responsibility for emergency code breaks to the subject in case an emergency treatment code break is required at a time when the investigator and backup are unavailable.

10.4 Subject Compliance

Each time study medication is dispensed subjects will be informed about compliance. When study medication is returned, compliance will be assessed based on the subject's interview and a count of the capsules. The investigator (or designee) will record the amount of study medication dispensed and returned at each visit, as well as document the reasons for non-compliance in the source document. The investigator will record the date and time of the study drug intake to the electronic data capture (EDC). The subject should be re-educated regarding treatment compliance and/or recording dose. A significant noncompliance with protocol or study drug will be communicated to the sponsor.

10.5 Study Treatment Accountability

Records shall be maintained of the delivery of study treatments to the study centres, the inventory at the study centres, the use of each subject and the return to the sponsor.

These records shall include dates, quantities, batch numbers, expiry dates, and the unique code numbers assigned to the study medication and to the study subjects.

The investigator shall be responsible for ensuring that the records adequately document that the subjects were provided the doses specified in the protocol and that all study medication received from the sponsor is reconciled. All study medication must be returned to the sponsor at the end of the study.

10.6 Contraception

There is potential to transfer BGS649 to a female partner through seminal fluid, with resulting theoretical risk to embryo-foetal development. Therefore, sexually active study subjects must use a double barrier method during vaginal sexual intercourse with women of child bearing potential while taking the study drug and for 3 months after completing the study treatment, even if the female partner is using a highly effective contraception, and should not father a child in this period. Single barrier (condom) should be used for non-vaginal penetrative intercourse with women of child bearing potential to prevent exposure of the partner to BGS649 through the semen and theoretical risk to an unborn child. This to be continued while taking the study drug and for 3 months after completing the study treatment. The subject should also not perform sperm donation while taking the study drug and for 3 months after completing the study treatment. A condom, together with a spermicide cream is required to be used in order to reduce risk of conception and to prevent delivery of the drug via the seminal fluid.

Seminal fluid samples will be collected after a minimum of 48 hours of sexual abstinence, therefore no sexual activity should be performed in this time period and no spermicidal cream used to avoid interference with seminal fluid evaluation.

10.7 Prohibited Therapy

The following classes of medication listed below are not permitted to be taken during the conduct of the study starting from Baseline. Over the counter or ordered via the internet or prescribed medications that are known to influence production or efficacy of sex hormones, or with oestrogen/androgen-like or antioestrogen/antiandrogen-like properties e.g.

- Opiates/Opioids including methadone for > 7 consecutive days during study duration
- Chronic systemic steroid treatment or systemic steroids for > 5 consecutive days for intercurrent illness (inhaled and topical steroids are allowed)
- Medications known to increase prolactin levels, e.g., antipsychotics
- 5- α -reductase inhibitors, e.g., Finasteride
- Spironolactone
- Cimetidine

- Growth hormone
- Testosterone, known testosterone enhancers, anabolic steroids, known active Fertility drugs and Oestrogens or selective oestrogen receptor modulators (SERMS)
- Clomid
- Bisphosphonates, Teriparatide, Denosumab (treatment with calcium and vitamin D for bone health is allowed at the discretion of the investigator)

11 ASSESSMENT OF EFFICACY

11.1 Efficacy and Pharmacokinetic Variables

1. Total and bioavailable testosterone, SHBG, FSH, LH
2. Body composition
 - Body weight and BMI
 - Waist circumference, hip circumference, and waist to hip ratio
 - Gynecomastia
 - Fat and muscle percentage (by impedance)
3. Cardiometabolic parameters
 - Blood pressure (diastolic blood pressure [DBP] and systolic blood pressure [SBP]) and heart rate
 - Fasting lipid panel (total cholesterol, low density lipoprotein [LDL], high density lipoprotein [HDL], triglycerides)
 - Glycosylated haemoglobin (HbA1c)
 - Fasting glucose and insulin
 - High sensitivity C-reactive protein (hs-CRP)
 - Homeostatic assessment of insulin resistance (HOMA-IR) (see [Section 11.2.3](#) for details)
4. PRO measures
 - International Index of Erectile Function (IIEF) and Patient-Reported Outcomes Measurement Information System® (PROMIS®) Sexual Function and Satisfaction (SexFS): to assess improvement in erectile function
 - IIEF and PROMIS SexFS: to assess improvement in sexual desire and satisfaction with sex life
 - 36-item Short Form Health Survey (SF-36): to assess general quality of life (QoL)
 - Brief Fatigue Inventory (BFI), PROMIS Fatigue Short Form, and the SF-36 Vitality: to assess improvement in energy levels

- Patient Global Impression of Status (PGI-S) items: to assess the subjects' overall impression of their current health status.
5. Actigraphy derived activity and sleep parameters
 - Counts of sedentary, moderate, and vigorous activity
 - Sleep quality and duration
 6. Dynamometry derived grip strength assessment
 7. PK semen analysis. Concomitantly with semen PK, plasma PK will be assessed to estimate plasma to semen BGS649 transference.

Detail of assessment of the efficacy and PK variables are presented in [Section 11.2](#) and [Section 11.3](#), respectively.

11.2 Efficacy Assessments

All efficacy assessments will be performed according to the schedule of assessments ([Table 9–1](#)).

11.2.1 Male Hormonal Parameters

Testosterone

Serum total testosterone and SHBG levels will be measured. Bioavailable testosterone will be calculated.

Serum total testosterone and SHBG laboratory parameters have to be taken before 11 am. If there is evidence that a sample has been inadvertently taken after this time, a retest is allowed after discussion with medical monitor.

Testosterone monitoring will be blinded to the subject, sponsor, and investigators and a decision about discontinuing BGS649/placebo will be made by an independent unblinded physician on a one to one basis after detailed evaluation of the subject ([Section 9.3.4](#) and [Section 16.3](#)). The subject may be discontinued if meeting testosterone discontinuation criteria as per section 9.3.4. It is important that investigators do not monitor testosterone independently of the study protocol as this will have the potential to inadvertently unblind the protocol. A subject may be withdrawn from the study if there was unblinded testosterone monitoring in addition what is described in the protocol.

Other Parameters

LH, and FSH will be assessed. In order not to unblind treatment assignment, these parameters will be blinded.

11.2.2 Body Composition

Body weight will be measured as part of the vital signs assessment ([Section 12.8](#)).

BMI

Body weight will be measured at the same time of day (\pm 30 minutes) at each assessment, before eating. Subjects should be instructed to wear similar clothing at each visit where

weight will be measured. Shoes and heavy accessories should be removed prior to measurement. Study staff should ensure that the same scale is used for the same subject at each assessment, and that the scales have been properly calibrated.

Height was measured at Screening in Study MBGS205 to enable BMI determination.

BMI is to be calculated from the height obtained at Screening in Study MBGS205. The BMI is calculated by dividing the measured subject weight by the square of the measured subject height, and is expressed in kg/m^2 .

Waist Circumference/Hip Circumference

Measurements will be performed to the nearest 0.1 cm.

The **waist measurement** (in cm) will be taken by measuring the distance around the narrowest part of the waist or, if this is not apparent, by measuring at the mid-point between the lowest rib and the top of the hip bone (iliac crest). The **hip measurement** (in cm) will be taken by measuring the distance around the largest extension of the buttocks and at the level of the bony prominences felt in the front of the hips.

The **waist to hip ratio** will be calculated by dividing the waist girth by the hip girth.

Measurements will preferably be performed using a flexible tape measure (provided for the study) and a non-permanent pen for marking the skin. If a plastic or cloth tape is used, it should be regularly checked against a metal tape to ensure that it has not stretched with prolonged use. Measurements should be made with the measuring tape placed firmly against the skin, but not so tight that it is compressing the skin. The tape should be placed so that it is lying flat and horizontal on the skin, parallel to the floor. Subjects should be asked to relax and exhale before the measurements are read.

Gynecomastia

Breast examination will be performed by palpation by an investigator. The subject will be in a supine position with hands behind their head. Investigators will perform a thorough examination of the breasts, noting their size and consistency, presence of any nipple discharge or axillary lymphadenopathy. The purpose is to look for or monitor enlargement or irregularities of glandular breast tissue. The investigator will then document the findings and, if gynecomastia is present, will document size of glandular breast tissue in centimetres/inches.

Body composition by bio-impedance

Bioelectrical impedance analysis estimates body composition. Measuring electrical impedance or opposition to the flow of an electric current through body tissues will be used to estimate and calculate subcutaneous and visceral body fat and proportion of muscle during the study.

The evaluation takes a few minutes. Subjects should be well hydrated (drinking water the night before and morning before assessment) and rested prior to the measurements as impedance is influenced by hydration and exercise.

11.2.3 Cardiometabolic Parameters

Blood pressure (SBP and DBP) will be measured as part of the vital signs analysis (Section 12.8).

All blood samples are to be collected after 8 hours fasting, after ECG and vital sign measurements

HbA1c, fasting lipids (total cholesterol, LDL, HDL, triglycerides), fasting glucose and insulin and hs-CRP will be measured. In addition, HOMA-IR will be calculated to estimate insulin resistance using the following formula:

$HOMA-IR = [\text{glucose (nmol/L)} * \text{insulin } (\mu\text{U/mL})/22.5]$, where glucose and insulin must be fasting (Matthews et al 1985).

11.2.4 Patient Reported Outcomes

The impact of BGS649 on various aspects of subject's health-related quality of life will be assessed using the following questionnaires. Ideally, PROs are to be evaluated before any other study activity is performed.

International Index of Erectile Function

The IIEF is a 15-item self-administered questionnaire, providing a quantitative index of erectile dysfunction severity by examining the following 5 relevant areas of sexual function (Rosen et al 1997; Cappelleri et al 2000):

1. Erectile function
2. Orgasmic function
3. Sexual desire
4. Intercourse satisfaction
5. Overall satisfaction.

Patient-Reported Outcomes Measurement Information System® Sexual Function and Satisfaction PROMIS® SexFS

The PROMIS SexFS PRO measure is an up to 19 item self-administered questionnaire compiled from relevant items in the PROMIS Sexual Function and Satisfaction domains (Flynn et al., 2013). The measure assesses global satisfaction with sex life (up to 7 items), erectile function (up to 6 items), interest in sexual activity (up to 4 items), and interfering factors (up to 2 items) in the last 30 days.

PROMIS® Fatigue Short Form

The PROMIS Fatigue Short Form measure is a 7-item self-administered questionnaire assessing the extent of fatigue and its impact on work and functioning in the last 7 days.

Brief Fatigue Inventory

The BFI is a 9-item self-administered questionnaire, providing an assessment of the severity of fatigue and its impact on the subject's ability to function at present and in the previous 24 hours (Mendoza et al., 1999).

36-Item Short Form Health Survey

The SF-36 QoL questionnaire is a multidimensional instrument that evaluates quality of life. It consists of questions assigned to the following categories (McHorney et al., 1994):

1. Vitality
2. Physical functioning
3. Bodily pain
4. General health perceptions
5. Physical role functioning
6. Emotional role functioning
7. Social role functioning
8. Mental health.

Patient Global Impression of Status items

Three patient global impression items (physical function, mental function, and sex life) will be included to assess the subjects' overall impression of their current health status and thus to evaluate the performance of the other PROs in this patient population. For full details of this assessment see Appendix II.

11.2.5 Actigraphy Derived Activity and Sleep Parameters

The Actigraph Link is a portable device that measures gross motor movements featuring a validated 3-axis accelerometer and data filtering technology that captures and records continuous, high resolution physical activity and sleep/wake information. It is a large, water-resistant wrist watch worn on the non-dominant hand.

Subjects will wear the monitor for 7 days consecutively after Visit 7, as described in the schedule of assessments ([Table 9-1](#)).

Activity parameters

Moderate and vigorous physical activity, sedentary bouts and activity counts will be measured. Software algorithms will be used to differentiate the amount of time spent at each of these activity levels. The cut-offs selected will be chosen to reflect the sedentary lifestyle of the subjects.

Sleep parameters

Time spent in sleep will be measured to enable assessment of sleep quality and duration.

11.2.6 Grip Strength Measurement

Grip strength assessment using a hand held dynamometer will be used as a surrogate measure of muscle strength. During this assessment, the subject will squeeze the device 3 times with each hand. An average of 3 measurements for each hand will be calculated and recorded.

11.3 Pharmacokinetic Assessments

Semen Pharmacokinetic sampling

Semen PK sampling for BGS649 will be performed at the following time points (excluding subjects that are vasectomised or have vasectomy planned during the study period), as defined in the schedule of assessments (Table 9-1): Baseline visit (Week 24 of Study MBGS205) and EOT (Visit 7).

Subjects that are discontinued early from the study drug will provide samples for seminal fluid PK at EOT (Visit 7) unless they are not able to provide this sample.

Semen samples for PK analysis will be centrifuged (1000 g × 10 minutes) and the separated seminal plasma will be stored at -20°C until samples are used.

Plasma Pharmacokinetic Sampling

Plasma PK sampling for BGS649 will be performed at the Baseline visit (Week 24 of Study MBGS205) and EOT (Visit 7) to estimate plasma to semen BGS649 transference.

12 ASSESSMENT OF SAFETY

The timing and frequency of safety assessments provided in [Table 9–1](#). For the primary and secondary safety endpoints see [Section 13.4.1](#) and [Section 13.4.2](#), respectively.

12.1 Adverse Events

12.1.1 Definitions

The definitions for AEs and SAEs are given below. It is of the utmost importance that all staff involved in the study are familiar with the content of this section. The principal investigator is responsible for ensuring this.

Adverse Event

An AE is defined as any untoward medical occurrence in a subject, or clinical investigation subject administered a pharmaceutical product, and which does not necessarily have a causal relationship with this treatment. An AE can therefore be any unfavourable and unintended sign, symptom or disease temporally associated with the use of a medicinal (investigation) product, whether or not related to the medicinal (investigational) product.

AEs/SAEs that resolve in Study MBGS205 will be recorded as a pre-existing condition/past medical or surgical history.

AEs will be recorded if there is a worsening of the pre-existing condition during study conduct with regard to nature, severity, or frequency or when there is new relevant occurrence. AEs ongoing from Study MBGS205 will be captured as AEs and followed accordingly.

An adverse drug reaction is an “untoward and unintended response to an investigational medicinal product related to any dose administered”.

All AEs judged by either the reporting investigator or the sponsor as having a reasonable causal relationship to a medicinal product qualify as adverse drug reactions. The expression of “reasonable causal relationship” means to convey in general that there are facts or arguments which suggest a causal relationship.

Serious Adverse Event

An SAE is defined as, but is not limited to, one that:

1. Results in death

Death is not an AE in itself, but an outcome. The cause of the death is the AE which resulted in death.

2. Is life-threatening

Life-threatening means that the subject was at immediate risk of death at the time of the SAE; it does not refer to an SAE that hypothetically might have caused death if it had been more severe.

3. Requires in-subject hospitalisation or prolongs existing hospitalisation

Hospitalisation is defined as at least 1 overnight formal admission into hospital, usually in order to perform additional tests, provide treatment which it is not possible to provide at home, and/or due to an unstable medical condition which requires specific monitoring of the subject. Pre-planned hospitalisations (known already prior to signing the ICF) will not be considered an SAE, unless any of the above criteria are fulfilled over the course of the hospitalisation due to unplanned complications. “Social” hospitalisation whereby it is administratively impossible to release the subject home is not necessarily an SAE. Complications that occur during hospitalisations are AEs. If the complication delays subject release from hospital, then the AE becomes an SAE.

4. Results in persistent or significant disability/incapacity

The term significant disability refers to any condition that impairs physical/physiological well-being to the extent that the subject is unable to function normally. Physical disability may include, but is not limited to, permanent disability of locomotion or motility, but also systemic permanent dysfunction including heart failure, liver insufficiency, or pulmonary fibrosis.

5. Is a congenital anomaly/birth defect

6. Is an important medical event

Important medical events that may not result in death, be life-threatening or require hospitalisation may be considered as an SAE when, based on appropriate medical judgement, they may jeopardise the subject, or the subject may require medical or surgical intervention to prevent one of the outcomes listed in this definition.

Treatment Emergent Adverse Event

Treatment emergent AEs (TEAEs) are defined as any AE occurring or worsening on or after the first dose of study medication administered during the study MBGS206

Adverse Events of Special Interest

Refer to [Section 12.1.7](#).

12.1.2 Recording of Adverse Events

For the purposes of this study, any detrimental change in the subject's condition, after signing the ICF and any unresolved AEs from MBGS205 up to 90 days after the last administration of study drug should be considered an AE.

The following variables will be recorded for each AE: verbatim/AE description and date for AE start and stop, severity, seriousness, causality rating, whether or not the AE caused the subject to discontinue, and the outcome. If the severity of the AE changes, a new AE must be recorded.

SAEs and AEs will be recorded after signing of the informed consent. All AEs/SAEs have to be reported, whether or not considered causally related to the investigational product or to the study procedure(s).

All ongoing AEs/SAEs should be followed up until resolution or stabilisation or the last visit if in the investigator's opinion, the AE is unlikely to resolve due to the subject's underlying disease.

At any time after the FU visit, if an investigator learns of an SAE that can be reasonably related to study drug, he/she should promptly notify the sponsor.

Intensity

The investigator will assess the intensity of AEs based on the following definitions:

1. Mild (awareness of sign or symptom, but easily tolerated)
2. Moderate (discomfort sufficient to cause interference with normal activities)
3. Severe (incapacitating, with inability to perform normal activities).

It is important to distinguish between serious and severe AEs. Severity is a measure of intensity whereas seriousness is defined by the criteria in [Section 12.1.8](#).

An AE of severe intensity need not necessarily be considered serious. For example, nausea that persists for several hours may be considered severe nausea, but not an SAE. On the other hand, a stroke that results in only a limited degree of disability may be considered a mild stroke but would be an SAE.

For an AE to be a suspected drug-related event there should be at least a reasonable possibility of a causal relationship between the study drug and the AE.

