13.5.5 Safety Analyses

The analysis of safety parameters will be based on the safety population. In general, missing safety data will not be replaced. A more detailed description will be presented in the SAP.

Adverse Events

AEs will be coded using the most recent version available of the Medical Dictionary for Regulatory Activities (MedDRA). Summaries will be by system organ class and preferred term. TEAEs are defined as any AE occurring or worsening on or after the first dose of study medication. Further details of this will be provided in a SAP. If a subject experiences the same preferred term multiple times, then the event will be counted only once and by the greatest severity.

The frequency and incidence of TEAEs will be presented by system organ class and preferred term for each treatment regimen (number and percentage of subjects experiencing at least 1 AE per preferred term as well as the number of observed events per preferred term). Separate tables will be presented by severity and by relationship. All AEs will be presented in full in a comprehensive listing including subject number, treatment regimen, severity, seriousness, action taken, outcome, relationship to treatment, onset/stop, and duration. Details of SAEs and AEs leading to withdrawal will be listed separately.

Concomitant Medication

Concomitant medication will be tabulated and summarised by treatment regimen.

Physical Examination

Physical examination results will be listed by subject and body system.

Vital Signs

Vital signs will be summarised as actual values and change from Baseline by treatment regimen and visit.

ECG

The overall ECG interpretation will be summarised by presenting the number and percentage of subjects with “Normal”, “Abnormal, not clinically significant”, and “Abnormal, clinically significant”.

ECG parameter values (e.g., QT_cF) will be summarised as actual values and change from Baseline by treatment regimen and visit to end of treatment.

Clinical Laboratory

Descriptive statistics will be presented for quantitative laboratory parameters for each treatment regimen and time-point. Similarly, changes from Baseline will be summarised.

Values outside the normal range will be categorised as H (above the normal range) or L (below the normal range) based on the laboratory’s reference range and these will be flagged in the listings of individual subject data.

Withdrawals

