### **7.1.4 Definitions relative to safety parameters**

#### **7.1.4.1 Adverse Event (AE)**

##### Treatment Emergent Adverse Event (TEAE)

A Treatment Emergent AE (TEAE) is defined as an AE occurring or worsening on or after the first dose of active study medication (from either MBGS205 or MBGS206).

TEAEs will also be split between AEs that start during the subject's active treatment period (for subjects randomised to active in MBGS205 this includes AE's starting in study MBGS205) and those that start on or after the first day of the MBGS206 follow-up period. A further category of TEAEs that started in MBGS206 but prior to the MBGS206 follow up period will also be utilised for summary tables (TEAEs started in MBGS205 would be excluded from this category).

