#### Notes:

- Two AEs with the same PT will be considered as two different events when calculating the “number of events” in the tables.
- Where a subject has the same AE, based on preferred terminology, reported multiple times in the same category the subject will only be counted once at the preferred terminology level in AE frequency tables.
- Where a subject has multiple AEs within the same SOC in the same category, the subject will only be counted once at the SOC level in AE frequency tables.
- AEs where the intensity is missing will be assumed to be “Severe”
- AEs where the causality is missing will be assumed to have “Reasonable possibility of relatedness”

An overall summary of AEs will be provided. The total number of events and number and proportion of subjects experiencing any AEs, TEAEs, TEAEs of special interest, AEs related to study medication (i.e where the investigator has recorded “Reasonable possibility of relatedness”), SAEs, SAEs related to study medication, severe AEs, AEs leading to permanent discontinuation of study treatment and AEs leading to death will be tabulated for each treatment regimen and overall.

Additionally, TEAEs, TEAEs of special interest, related TEAEs, serious TEAEs, related SAEs, AEs leading to permanent discontinuation of study treatment and AEs leading to death will be summarised by SOC and PT for each treatment regimen and overall (number and percentage of subjects experiencing at least one AE per PT as well as the number of observed events per PT). All TEAEs will also be summarised separately by maximum intensity for each SOC and PT and by causality for each SOC and PT.

A table presenting the number and percentage of subjects with at least one AE and the number of AEs for the most common treatment-emergent AEs (reported in  $\geq 1\%$  of patients in any treatment regimen) will be provided. PTs will be used for tabulation, sorted by decreasing overall frequency.

All AEs will be presented in full in a comprehensive listing including subject number, treatment regimen, intensity, seriousness, actions taken, outcome, causality, onset/stop and duration. Details of all TEAEs of special interest, SAEs, AEs leading to permanent discontinuation of study treatment and AEs leading to death will be listed separately.

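### A new AE record for every severity change, with no rule in the SAP to link records of one episode, inflates event counts and leaves the treatment-emergent status of easing AEs undefined

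*Protocol*

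**What the plan says.** **Recording.** Protocol 12.1.2 lists the variables held for each AE, among them "verbatim/AE description and date for AE start and stop, severity, seriousness, causality rating". No field tying one record to another is listed. It then requires: "If the severity of the AE changes, a new AE must be recorded". The direction of change is not restricted. For AEs carried over from the parent study, Protocol 12.1.1 says: "AEs ongoing from Study MBGS205 will be captured as AEs and followed accordingly".

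**Counting.** The notes in SAP 8.7.4 state, for the number-of-events columns: "Two AEs with the same PT will be considered as two different events". For subject counts, repeated reports of a preferred term in the same category are handled so that "the subject will only be counted once at the preferred terminology level in AE frequency tables". Protocol 13.5.5 has a similar rule for a repeated preferred term, "then the event will be counted only once and by the greatest severity", but also tabulates the number of events observed per preferred term.

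**Treatment-emergent status.** SAP 7.1.4.1 says: "A Treatment Emergent AE (TEAE) is defined as an AE occurring or worsening on or after the first dose of active study medication". For men who had placebo in MBGS205, the first active dose is the first MBGS206 dose (Protocol 13.5.3.1; SAP 8.1.5). SAP 7.1.4.1 also separates TEAEs starting in follow-up, and defines an MBGS206 treatment-period category from which events begun in MBGS205 are left out.

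**Duration.** SAP 7.1.4.1 computes duration for each AE as resolution date minus start date plus 1. SAP 8.7.4 shows it in the AE listing.

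**The concern.** The recording rule and the counting rule are each workable alone. Together they make the number of events depend on how often severity is re-graded, and not only on how often something happens to a subject. A fluctuating AE then looks like several AEs.

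Treatment-emergent status raises a second question. Each record holds one severity, so worsening appears in the data only as a further record. A flag based on start date would catch that record, but it would also catch one opened because the AE improved. The SAP does not tell the programmer to compare the new severity with the pre-dose severity. Safety data in men switching from placebo are a stated objective, and TEAEs in those men are a secondary endpoint. Charging resolving placebo-period AEs to BGS649 would distort that description against the drug.

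**Working it through.** The plan states no figure to reproduce. The check follows one episode through the rules.

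**Event counts.** Inputs: one record per severity level held (Protocol 12.1.2) and one event per record (SAP 8.7.4).

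Events counted per episode = 1 + k, where k is the number of severity changes.

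| Severity changes, k | Events counted | True episodes |
|---|---|---|
| 0 | 1 | 1 |
| 1 | 2 | 1 |
| 2 (e.g. mild–moderate–mild) | 3 | 1 |
| 3 | 4 | 1 |

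With an average of m changes per episode, N episodes appear as N × (1 + m) events. The documents give no value for m. Assuming 0.10 to 0.25 would give 10% to 25% inflation, but that only restates the assumption. The subject still counts once for that preferred term in that category. Each record also carries its own shorter duration in the listing.

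**Easing AE in a placebo switcher (assumed dates).** A moderate AE starts 30 days before the first BGS649 dose and becomes mild 10 days after it.

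- Record 1 (moderate) starts before active drug and is not a TEAE.
- Record 2 (mild), if it starts on the date of change, occurs after the first active dose. It adds 1 TEAE event and 1 subject to the TEAE numerator, where the true episode adds 0 and 0.
- Record 2, if it keeps the original onset date, neither occurs nor worsens after the dose, and adds 0 and 0.

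The result turns on a start-date convention that neither document states. In a switch group of n men, one such man adds 100/n percentage points to that preferred term. The documents give no n for these groups.

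**Easing AE in a continuing man.** An AE that began on active drug in MBGS205 is already a TEAE, so his overall TEAE incidence is unchanged. If it eases in MBGS206 and the new record takes the date of change, that record falls in the MBGS206 category meant to leave out MBGS205 onsets. Easing after treatment places a record in the follow-up category in the same way. The once-per-term rule works within a category, so it does not prevent either.

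**The case against.** The case on the other side has real force on scope.

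- **Improvement need not be an occurrence.** Protocol 12.1.2 describes an AE as a detrimental change, Protocol 12.1.3 offers an outcome code for a resolving event, and the TEAE definition speaks of worsening. Sites also follow eCRF instructions (Protocol 17.1) that are not in these documents. This stands: a reader might infer that easing placebo-period AEs become BGS649 TEAEs, but the documents do not say so. A date-of-change start is the natural reading, because every AE has its own start date, but it remains a reading.
- **Not every AE table is affected.** A reader might infer that all AE output is wrong. Subject counts are protected within a category, severity summaries use maximum intensity, and duration is only listed. This also stands.
- **Double capture is not shown.** A reader might infer that AEs ongoing at the switch are entered twice and then pooled. Protocol 12.1.1 says only that they are captured and followed, and the schedule of assessments includes AE assessment among the items transferred from MBGS205.
- **The protocol already collapses repeats.** Its once-at-greatest-severity rule could be read that way. But the same section also reports the number of events per preferred term, and the SAP note counts same-term AEs separately. This does not remove the event-count problem.
- **Low stakes.** All analyses are exploratory, the bone-density endpoint is untouched, and the full AE listing lets a reader see split episodes. This limits the importance but does not correct the tables.

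**Conclusion.** The event-count part is firm: followed as written, the two rules overstate the number of events by one for every severity change, and they split the listed durations. The TEAE and period-table part is conditional. It arises if a severity-change record starts on the date of change and the TEAE rule is applied record by record. It would then affect subject incidence in the placebo-switch groups and in the MBGS206 and follow-up tables, and not overall TEAE incidence in continuing men. The overall size cannot be computed without rates of severity change and of AEs ongoing at the switch. The point merits a correction to the SAP; it does not threaten the primary analysis.

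**What to change.** Add to SAP 7.1.4.1 and 8.7.4:

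1. For event counts and durations, treat contiguous records of the same preferred term in a subject (for example, a start no later than one day after the previous stop) as one episode, including records continued from MBGS205.
2. Class an episode as treatment-emergent only if it first starts on or after the first active dose, or if its severity then rises above the last pre-dose severity.
3. Tabulate intensity as the maximum on or after the first active dose, leaving out placebo-period severity.
4. In the MBGS206 and follow-up period tables, count an episode only if, within that period, it starts or its severity rises above the level at period entry.
5. State the start-date convention for severity-change records. Where partial dates prevent linking, keep the existing default in SAP 7.2.2.4 of treating the event as treatment-emergent.

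Items 3 and 4 are needed because collapsing to first onset and overall maximum intensity would create new errors. An AE severe on placebo, mild at the switch and then moderate on BGS649 would be tabulated as a severe TEAE. A continuing man's worsening in MBGS206 would be moved back to an MBGS205 onset and drop out of the MBGS206 table.

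The cost is SAP text and a collapsing step in the AE programming, with no new data collection. True back-to-back recurrences would be merged in the event counts; all raw records stay in the listings.
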